5.2.3 Study Termination

If the study is prematurely terminated by the sponsor, any regulatory authority, or the investigator for any reason, the investigator will promptly inform the study participants and assure appropriate therapy or follow-up for the participants, as necessary. The investigator will provide a detailed written explanation of the termination to the IRB/ Independent Ethics Committee (IEC).

6 STUDY PROCEDURES

Complete study schedule details listed by type of visit are described below. Refer also to [APPENDIX A: Schedule of Study Procedures and Evaluations](#).

6.1 Screening

6.1.1 Visit 00A, Screening Clinic Visit (Day -28 to -7)

- Participants will be provided with a description of this trial (purpose and study procedures) and asked to read and sign the ICF. The ICF will be signed prior to performing any study procedures.
- Eligibility criteria will be reviewed with the participant.
- Demographic variables (age, gender, race and ethnicity) and screening characteristics (height and weight) will be collected.
- Complete medical history will be obtained by interview of the participant to ensure eligibility.
- All concomitant medications taken within 30 days prior to signing the ICF will be reported on the appropriate Data Collection Form (DCF).
- Oral temperature, sitting blood pressure, and sitting pulse will be obtained. Participants must not eat or drink anything hot or cold within 10 minutes prior to taking oral temperature.
- A complete physical examination will be performed on all participants by a study clinician licensed to make medical diagnoses and listed on the Form FDA 1572 as the site PI or sub-investigator.
- A 12-lead ECG will be performed.
- Height and weight will be obtained for BMI calculations.
- Approximately 10 mL of venous blood will be collected for safety laboratory assessments including Hgb, BUN, serum creatinine (includes eGFR), ALT, AST, total bilirubin, serum potassium, and serum magnesium.
- Approximately 12 mL of venous blood will be collected for HCV, hepatitis B surface antigen (HBsAg), and HIV testing.
- Advise to refrain from alcohol use for at least 72 hours before admission.

6.1.2 Visit 00B, 2nd Screening Clinic Visit (Day -28 to -7)

- Participant's willingness to participate will be reconfirmed and documented in the participant's study source document records prior to performing any further study procedures.

- A urine pregnancy test will be performed on all women of childbearing potential and must be negative to ensure eligibility.
- Urine screen for drugs.
- Approximately 6 mL of venous blood will be collected to screen for alcohol or breath collection if breathalyzer is used for alcohol testing
- Remind to refrain from use of alcohol for 72 hours prior to hospital admission.

6.1.3 Visit 00C, Hospital Admission, Day -1

- Participants will be admitted to the hospital 12-24 hours before administration of study product.
- Participant's willingness to participate will be reconfirmed and documented in the participant's study source document records prior to performing any further study procedures.
- Eligibility criteria will be reviewed with the participant.
- Interim medical history, including an assessment for new medical conditions and stability of chronic diseases, will be obtained by interview of participants and any changes since the first visit (Visit 00A) will be noted.
- All concomitant medications will be reviewed with participants prior to the administration of study medication. Any new concomitant medications taken since the screening visit will be reviewed with participants and assessed for continued eligibility.
- A urine pregnancy test will be performed on all women of childbearing potential and must be negative to ensure eligibility.
- Urine screen for drugs.
- Approximately 6 mL of venous blood will be collected to screen for alcohol or breath collection if a breathalyzer is used for alcohol testing.
- Alcohol and urine drug screening will be performed, and results will be checked when available. Participants with positive results will be discharged unless the participants are on approved prescriptions. However, opiates and benzodiazepines, which are CYP3A4 substrates, will not be allowed even if prescribed. Participants who are discharged because of a positive alcohol or urine drug screen will not be rescreened for enrollment.
- If applicable, a peripheral intravenous catheter will be placed at this Visit or Visit 01A for participants with negative alcohol and drug screening except for participants who are on approved prescriptions. However, opiates and benzodiazepines, which are CYP3A4 substrates, will not be allowed even if prescribed.
- Participants will be reminded that they must fast overnight (i.e., at least 8 hours). Participants will be required to bring in from home all their medications they take at home.

6.2 Dosing (Day 1) and In-house Confinement/ PK Collection

6.2.1 Visit 01A, Administration of Study Product

- Eligibility criteria will be reviewed.
- Interim medical history, including an assessment for new medical conditions and stability of chronic diseases, will be obtained by interview of participants and any changes since the previous visit (Visit 00C) will be noted.
- Alcohol and urine drug screening results from Day -1 will be checked for participants whose alcohol and drug screening results were not available on time and who are not discharged on Day -1. Participants with positive results will be discharged unless the participants are on approved prescriptions. However, opiates and benzodiazepines, which are CYP3A4 substrates, will not be allowed even if prescribed. Participants who are discharged because of a positive alcohol or urine drug screen will not be rescreened for enrollment.
- Vital signs, including oral temperature, sitting pulse, and sitting blood pressure, will be obtained to ensure eligibility of participants with negative alcohol and urine drug screening results.
- If applicable, a peripheral intravenous catheter will be placed if not already placed on Visit 00C.
- A targeted physical examination may be performed prior to administration of study product, if indicated based on review of complete medical history and any updates obtained by interview of participants since the screening visit, by a study clinician licensed to make medical diagnoses and listed on the Form FDA 1572 as the site PI or sub-investigator.
- All concomitant medications will be recorded on the appropriate DCF.
- Collect and measure urine volume for PK up to 1 hour pre-dose and again after the dose has been administered; urine will be collected in collection beakers at 1 hour pre-dose and at intervals 0-4, 4-8, 8-12, 12-24, 24-48, 48-72, and 72-96 hours post-dose. Urine volume will be measured and recorded for each of these time intervals. Urine will be stored at room temperature and then frozen at -20°C within 24 hours. Urine will be in ≤100 mL aliquots and stored at -20°C until shipped to Fisher Bioservices for storage. Fisher Bioservices will ship samples to bioanalytical laboratory for concentration measurements.
- A urine pregnancy test will be performed prior to administration of the study product on all women of childbearing potential. Results must be negative and known prior to receipt of the study product.
- Approximately 4 mL of venous blood will be collected for PK prior to administration of study product (up to 1 hour pre-dose).
- Participants should start the recommended meal (high-fat and high-calorie, <https://www.fda.gov/media/121313/download>) 30 minutes prior to administration of

pretomanid. Study participants should eat this meal in 30 ± 10 minutes or less; however, pretomanid should be administered 30 ± 10 minutes after start of the meal.

- Participants will receive one dose of 200 mg pretomanid orally with 240 mL water under direct supervision and a mouth check will be done. If a participant meets eligibility criteria and is admitted, but is not dosed, the participant may be re-evaluated for participation in the study.
- Liquids, food, and medicine will not be allowed until at least 2 hours after dosing.
- All AEs/Serious Adverse Events (SAEs) will be recorded on the appropriate DCF/DMID SAE Report Form.

6.2.2 Visit 01B, Day 1, Time 1 Hour \pm 10 Minutes Post-dose; Hospital Stay

- A targeted physical examination may be performed if indicated based on new symptoms after administration of study product, by a study clinician licensed to make medical diagnoses and listed on the Form FDA 1572 as the site PI or sub-investigator.
- All concomitant medications will be recorded on the appropriate DCF.
- Collect all urine for PK, measure and record urine PK volume, aliquot, label and freeze per [Section 7.2.2.1](#).
- Approximately 4 mL of venous blood will be collected for PK.
- All AEs/Serious Adverse Events (SAEs) will be recorded on the appropriate DCF/DMID SAE Report Form.

6.2.3 Visit 01C, Day 1, Time 2 Hours \pm 10 Minutes Post-dose; Hospital Stay

- A targeted physical examination may be performed if indicated based on new symptoms after administration of study product, by a study clinician licensed to make medical diagnoses and listed on the Form FDA 1572 as the site PI or sub-investigator.
- All concomitant medications will be recorded on the appropriate DCF.
- Collect all urine for PK, measure and record urine PK volume, aliquot, label and freeze per [Section 7.2.2.1](#).
- Approximately 4 mL of venous blood will be collected for PK.
- All AEs/SAEs will be recorded on the appropriate DCF/DMID SAE Report Form.

6.2.4 Visit 01D, Day 1, Time 4 Hours ± 10 Minutes Post-dose; Hospital Stay

- A targeted physical examination may be performed if indicated based on new symptoms after administration of study product, by a study clinician licensed to make medical diagnoses and listed on the Form FDA 1572 as the site PI or sub-investigator.
- All concomitant medications will be recorded on the appropriate DCF.
- Collect all urine for PK, measure and record urine PK volume, aliquot, label and freeze per [Section 7.2.2.1](#).
- Approximately 4 mL of venous blood will be collected for PK.
- All AE/SAEs will be recorded on the appropriate DCF/DMID SAE Report Form.

6.2.5 Visit 01E, Day 1, Time 5 Hour ± 10 Minutes Post-dose; Hospital Stay

- A targeted physical examination may be performed if indicated based on new symptoms after administration of study product, by a study clinician licensed to make medical diagnoses and listed on the Form FDA 1572 as the site PI or sub-investigator.
- All concomitant medications will be recorded on the appropriate DCF.
- Collect all urine for PK, measure and record urine PK volume, aliquot, label and freeze per [Section 7.2.2.1](#).
- Approximately 4 mL of venous blood will be collected for PK.
- All AEs/SAEs will be recorded on the appropriate DCF/DMID SAE Report Form.

6.2.6 Visit 01F, Day 1, Time 6 Hours ± 10 Minutes Post-dose; Hospital Stay

- A targeted physical examination may be performed if indicated based on new symptoms after administration of study product, by a study clinician licensed to make medical diagnoses and listed on the Form FDA 1572 as the site PI or sub-investigator.
- All concomitant medications will be recorded on the appropriate DCF.
- Collect all urine for PK, measure and record urine PK volume, aliquot, label and freeze per [Section 7.2.2.1](#).
- Approximately 4 mL of venous blood will be collected for PK.
- All AEs/SAEs will be recorded on the appropriate DCF/DMID SAE Report Form.

6.2.7 Visit 01G, Day 1, Time 8 Hour ± 10 Minutes Post-dose; Hospital Stay

- A targeted physical examination may be performed if indicated based on new symptoms after administration of study product, by a study clinician licensed to make medical diagnoses and listed on the Form FDA 1572 as the site PI or sub-investigator.
- All concomitant medications will be recorded on the appropriate DCF.
- Collect all urine for PK, measure and record urine PK volume, aliquot, label and freeze per [Section 7.2.2.1](#).
- Approximately 4 mL of venous blood will be collected for PK.
- All AE/SAEs will be recorded on the appropriate DCF/DMID SAE Report Form.

6.2.8 Visit 01H, Day 1, Time 12 Hours ± 10 Minutes Post-dose; Hospital Stay

- Vital signs, including oral temperature, sitting blood pressure, and sitting pulse will be obtained. Participants must not eat or drink anything hot or cold within 10 minutes prior to taking oral temperature.
- A targeted physical examination may be performed if indicated based on new symptoms after administration of study product, by a study clinician licensed to make medical diagnoses and listed on the Form FDA 1572 as the site PI or sub-investigator.
- All concomitant medications will be recorded on the appropriate DCF.
- Collect all urine for PK, measure and record urine PK volume, aliquot, label and freeze per [Section 7.2.2.1](#).
- Approximately 4 mL of venous blood will be collected for PK.
- All AEs/SAEs will be recorded on the appropriate DCF/DMID SAE Report Form.

6.2.9 Visit 01I, Day 1, Time 16 Hour ± 10 Minutes Post-dose; Hospital Stay

- A targeted physical examination may be performed if indicated based on new symptoms after administration of study product, by a study clinician licensed to make medical diagnoses and listed on the Form FDA 1572 as the site PI or sub-investigator.
- All concomitant medications will be recorded on the appropriate DCF.
- Collect all urine for PK, measure and record urine PK volume, aliquot, label and freeze per [Section 7.2.2.1](#).
- Approximately 4 mL of venous blood will be collected for PK.
- All AE/SAEs will be recorded on the appropriate DCF/DMID SAE Report Form.

6.2.10 Visit 01J, Day 2, Time 24 Hour ± 1 Hour Post-dose; Hospital Stay

- Vital signs, including oral temperature, sitting blood pressure, and sitting pulse will be obtained. Participants must not eat or drink anything hot or cold within 10 minutes prior to taking oral temperature.
- A targeted physical examination may be performed if indicated based on new symptoms after administration of study product, by a study clinician licensed to make medical diagnoses and listed on the Form FDA 1572 as the site PI or sub-investigator.
- All concomitant medications will be recorded on the appropriate DCF.
- Collect all urine for PK, measure and record urine PK volume, aliquot, label and freeze per [Section 7.2.2.1](#).
- Approximately 4 mL of venous blood will be collected for PK.
- All AEs/SAEs will be recorded on the appropriate DCF/DMID SAE Report Form.

6.2.11 Visit 01K, Day 2, Time 36 Hour ± 1 Hour Post-dose; Hospital Stay

- A targeted physical examination may be performed if indicated based on new symptoms after administration of study product, by a study clinician licensed to make medical diagnoses and listed on the Form FDA 1572 as the site PI or sub-investigator.
- All concomitant medications will be recorded on the appropriate DCF.
- Collect all urine for PK, measure and record urine PK volume, aliquot, label and freeze per [Section 7.2.2.1](#).
- Approximately 4 mL of venous blood will be collected for PK.
- All AEs/SAEs will be recorded on the appropriate DCF/DMID SAE Report Form.

6.2.12 Visit 01L, Day 3, Time 48 Hours ± 1 Hour Post-dose, Hospital Stay

- A targeted physical examination may be performed if indicated based on new symptoms after administration of study product, by a study clinician licensed to make medical diagnoses and listed on the Form FDA 1572 as the site PI or sub-investigator.
- All concomitant medications will be recorded on the appropriate DCF.
- Vital signs, including oral temperature, sitting blood pressure, and sitting pulse will be obtained. Participants must not eat or drink anything hot or cold within 10 minutes prior to taking oral temperature.
- Collect all urine for PK, measure and record urine PK volume, aliquot, label and freeze per [Section 7.2.2.1](#).

- Approximately 4 mL of venous blood will be collected for PK.
- If applicable, the intravenous catheter will be removed by a nurse or physician.
- Provide urine PK collection instructions and containers. Instruct the participant to collect urine for 2 more days at home and keep urine container at room temperature with the cap on.
- Discharge after review by physician licensed to make medical diagnoses and listed on the Form FDA 1572 as the site PI or sub-investigator. Note: Participants may remain in the hospital per site decision.
- All AEs/SAEs will be recorded on the appropriate DCF/DMID SAE Report Form.

6.3 Follow-Up

6.3.1 Visit 01M, Day 4, Time 72 Hours ± 4 Hours Post-dose, Clinic Visit or Continued Hospital Stay, per Site Decision

- Interim medical history, including an assessment for new medical conditions and stability of chronic diseases, will be obtained by interview of participants and any changes since the previous visit will be noted.
- A targeted physical examination may be performed if indicated based on review of interim medical history, by a study clinician licensed to make medical diagnoses and listed on the Form FDA 1572 as the site PI or sub-investigator.
- All concomitant medications will be recorded on the appropriate DCF.
- Vital signs, including oral temperature, sitting blood pressure, and sitting pulse will be obtained. Participants must not eat or drink anything hot or cold within 10 minutes prior to taking oral temperature.
- Receive home urine collected jug from subject. Measure and record urine PK volume, aliquot, label and freeze per [Section 7.2.2.1](#).
- Provide urine PK collection container and remind the participant to collect urine at home and keep urine container at room temperature with cap on for PK.
- Approximately 4 mL of venous blood will be collected for PK.
- All AE/SAEs will be recorded on the appropriate DCF/DMID SAE Report Form.

6.3.2 Visit 01N, Day 5, Time 96 Hours ± 4 Hours Post-dose, Clinic Visit or Continued Hospital Stay, per Site Decision

- Interim medical history, including an assessment for new medical conditions and stability of chronic diseases, will be obtained by interview of participants and any changes since the previous visit will be noted.
- A targeted physical examination may be performed if indicated based on review of interim medical history, by a study clinician licensed to make medical diagnoses and listed on the Form FDA 1572 as the site PI or sub-investigator.
- All concomitant medications will be recorded on the appropriate DCF.
- Vital signs, including oral temperature, sitting blood pressure, and sitting pulse will be obtained. Participants must not eat or drink anything hot or cold within 10 minutes prior to taking oral temperature.
- A 12-Lead ECG will be performed.
- Receive home urine collected jug from subject. Measure and record urine PK volume, aliquot, label and freeze per [Section 7.2.2.1](#).
- Approximately 4 mL of venous blood will be collected for PK.
- All AE/SAEs will be recorded on the appropriate DCF/DMID SAE Report Form.
- Approximately 10 mL of venous blood will be collected for safety laboratory assessments including Hgb, BUN, serum creatinine (includes eGFR), ALT, AST, total bilirubin, serum potassium, and serum magnesium.
- If hospitalization was continued, discharge after review by physician licensed to make medical diagnoses and listed on the Form FDA 1572 as the site PI or sub-investigator.

6.3.3 Visit 02, Day 12 ± 2 Days Post-dose, Clinic Visit

- Interim medical history, including an assessment for new medical conditions and stability of chronic diseases, will be obtained by interview of participants and any changes since the previous visit will be noted.
- A targeted physical examination may be performed on all participants by a study clinician licensed to make medical diagnoses and listed on the Form FDA 1572 as the site PI or sub-investigator.
- All concomitant medications will be recorded on the appropriate DCF.

- Vital signs, including oral temperature, sitting blood pressure, and sitting pulse will be obtained. Participants must not eat or drink anything hot or cold within 10 minutes prior to taking oral temperature.
- A urine pregnancy test will be performed on all women of childbearing potential.
- All AE/SAEs will be recorded on the appropriate DCF/DMID SAE Report Form.
- Approximately 10 mL of venous blood will be collected for safety laboratory assessments including Hgb, BUN, serum creatinine (includes eGFR), ALT, AST, total bilirubin, serum potassium, and serum magnesium.

6.4 Final Visit, Visit 03, Day 85+7 Days Post-dose, Phone Visit

- The participant will be asked if they or their partner became pregnant. If the participant became pregnant, the Pregnancy Report and Follow-Up forms will be completed. If the participant's partner became pregnant, details about the pregnancy should be reported to the sponsor to document the outcome of the pregnancy. All SAEs will be recorded on the appropriate DCF/DMID SAE Report Form.

6.5 Early Termination Visit (if needed)

The following activities will be performed at the early termination (ET) visit on participants who withdraw, or are withdrawn or terminated from this trial:

- Obtain interim medical history, including an assessment of new symptoms and conditions from the patient, and note any changes since the previous visit.
- A targeted review of systems. For participants with renal impairment, this targeted review of systems will also focus on renal disease and will include questions pertaining to changes in the frequency and volume of urine, requirement for dialysis, and mental status.
- Targeted physical examination, if needed.
- All concomitant medications will be recorded on the appropriate DCF.
- Assess for AEs/SAEs.
- Urine pregnancy test for females of childbearing potential.
- Vital signs including oral temperature, sitting blood pressure, and sitting pulse will be obtained.
- Approximately 10 mL of venous blood will be collected for safety laboratory assessments including Hgb, BUN, serum creatinine (includes eGFR), ALT, AST, total bilirubin, serum potassium, and serum magnesium.

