3.3 Study Endpoints or Outcome Measures

3.3.1 Primary

3.3.1.1 Plasma PK of Pretomanid (see [Section 10.5](#) for specific PK parameters)

The plasma PK of a single dose of pretomanid will be assessed from serial blood samples collected up to 1 hour pre-dose (Day 1) and at multiple time points post dosing: 1, 2, 4, 5, 6, 8, 12, 16, 24, 36, 48, 72, and 96 hours. The primary outcome measure will be total plasma concentration of pretomanid.

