3.3.1.2 Urine PK of Pretomanid (see [Section 10.5](#) for specific PK parameters)

The urine PK of a single dose of pretomanid will be assessed from urine collected up to 1 hour pre-dose, 0-4, 4-8, 8-12, 12-24, 24-48, 48-72, and 72-96 hours post-dose. Volume of urine will be measured and recorded at each of these time intervals. Urine samples will be stored at room temperature and then frozen at -20°C within 24 hours. Urine samples will be stored in ≤ 100 mL aliquots at -20°C until shipped to Fisher Bioservices for storage.

The concentrations of pretomanid in plasma and urine will be measured by the validated bioanalytical methods. The pretomanid PK profiles in plasma and urine estimated through a non-compartmental analysis.

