3.3.2 Secondary

- Safety – Number of participants reporting AEs. (Time Frame: Time of dosing [Day 1] to Day 12).
- Safety – Mean change from baseline in hemoglobin (Hgb), alanine aminotransferase (ALT), aspartate aminotransferase (AST), total bilirubin, blood urea nitrogen (BUN), creatinine (includes eGFR), serum potassium and magnesium (Time Frame: Screening [Days -28 to -7], Day 5 and Day 12).
- Safety – Mean change from baseline in oral temperature, pulse, and sitting blood pressure (Time Frame: Day 1 [pre-dose], 12 hours, 24 hours, 48 hours, 72 hours, 96 hours, and Day 12).
- Safety – Mean change from baseline in ECG corrected QT interval by Fridericia (QTcF) (Time Frame: Screening [Days -28 to -7] and Day 5).
- The concentrations of pretomanid metabolites (M19 and M50) in plasma will be measured by validated bioanalytical methods. PK – area under the plasma concentration-time curve from time 0 to the last measurement (AUC_{last}), and any other parameters considered to be of interest, of representative metabolites M19 and M50 in plasma (Time Frame: Up to 96 hours post-dose).
- Excretion of representative metabolites M19 and M50 in urine. The amounts of M19 and M50 will be calculated in urine (i.e., M19 and M50 concentrations measured using validated bioanalytical methods multiplied by collected urine volume).

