5.2 Withdrawal from the Study or Study Termination

5.2.1 Withdrawal from the Study

Participants may voluntarily withdraw their consent for trial participation at any time and for any reason, without penalty.

A participant may withdraw or be withdrawn from this trial for any of the following reasons:

- Medical disease or condition, or any new clinical finding for which continued participation, in the opinion of the site PI or appropriate sub-investigator, would compromise the safety of the participant, or would interfere with the participant's successful completion of this trial, or would interfere with the evaluation of data.
- Participant no longer meets eligibility criteria (see [Section 5.1](#)).
- As deemed necessary by the site PI or appropriate sub-investigator for noncompliance or other reasons.
- Withdrawal of consent.
- Lost to follow-up (defined as 3 unsuccessful attempts to contact the participant; the methods and dates contact was attempted will be documented).
- Termination of this trial.

A participant who is withdrawn or voluntarily withdraws from the study for any reason, whether related to the study drug or not, after having received the study drug, will be considered an early termination subject. The PI or sub-investigator will make every effort to ensure that early termination

participants who have received the study drug complete the early termination assessments and safety follow-up assessments.

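### The early termination visit takes safety blood but no PK sample and does not receive home urine, so unreplaced participants who leave between 24 h and 96 h lose AUClast and urine data that it could partly recover (minor)

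*Protocol*

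**What the plan says.** Protocol Section 6.5 opens with "The following activities will be performed at the early termination (ET) visit on participants who withdraw, or are withdrawn or terminated from this trial". It then lists interim history, review of systems, a targeted examination if needed, medications, adverse events, a pregnancy test, vital signs and safety laboratory tests. The only blood is this: "Approximately 10 mL of venous blood will be collected for safety laboratory assessments including Hgb, BUN, serum creatinine". PK blood, PK urine and an ECG are not on the list. In Appendix A the PK blood and PK urine rows end at Visit 01N.

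The neighbouring sections do not fill the gap:

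- Section 5.2.1 asks sites to make every effort that "participants who have received the study drug complete the early termination assessments and safety follow-up assessments". PK follow-up is not mentioned.
- Section 5.2.2 replaces dosed participants who withdraw before 24 h, but generally not those who leave later.
- Section 6.6 allows unscheduled visits for safety, repeat laboratory tests and pregnancy testing.
- SAP Section 6.5 uses no missing-data method apart from completing partial or missing dates.

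The primary plasma endpoint uses samples at "1, 2, 4, 5, 6, 8, 12, 16, 24, 36, 48, 72, and 96 hours", and the primary urine endpoint uses the intervals "0-4, 4-8, 8-12, 12-24, 24-48, 48-72, and 72-96 hours post-dose". At 48 h (Section 6.2.12) sites are told: "Instruct the participant to collect urine for 2 more days at home". The containers are handed in at Visits 01M and 01N, where the instruction is "Receive home urine collected jug from subject". The only scheduled post-dose ECG is also at Visit 01N.

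**The concern.** Someone who goes home at 48 h, withdraws and attends the early termination visit is seen and has blood drawn. Under the listed procedures no PK tube is filled, and urine already collected has no receiving visit.

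AUClast runs to the last quantifiable sample (SAP Section 3.3.1), so a shortened series biases it low. It is one of the two AUC measures named in Protocol Section 10.1 for the Part A decision. The extrapolated share of AUC∞ rises, and cumulative urinary excretion stops early. SAP Section 6.3.2.1 also contemplates that a participant with estimable plasma parameters may be left out of the PK population because of problems with urine data. With six per group and no replacement after 24 h, little else offsets these losses.

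An off-schedule plasma sample needs no new rule to be usable, because Protocol Section 10.5.2 and SAP Section 10.2.2.1 both compute parameters from actual times.

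**Working it through.** **The plan's own figures first.** Protocol Section 10.2 assumes six per group, a CV of 20% and a true ratio of 2.0.

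- Log-scale SD = √ln(1 + 0.20²) = 0.198. SE of the log ratio = 0.198 × √(2/6) = 0.1143.
- P(observed ratio ≥ 1.5) = Φ(ln(2/1.5)/0.1143) = 99.4%. The plan states more than 99%.
- P(lower 90% bound ≥ 1.5) = 69.7% with a noncentral t on 5 df (matched pairs). The plan states about 70%. An unpaired analysis on 10 df gives 75.7%.

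These figures are context. The point does not dispute them.

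**Inputs for the truncation.**

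- Half-life about 18 h (Protocol Section 2.1.5.2).
- Half-life 36 h is an assumption, to show slower clearance. The documents give no value for renal impairment.
- Tmax 5 h is assumed. Section 2.1.5.2 gives 4 to 5 h fasted and about 1 h later with a high-fat meal. Using 5.5 h moves the shares of AUC∞ at 48 h and 72 h by at most 0.2 percentage points.
- One-compartment oral model, k = ln 2 / half-life, with ka solved from ln(ka/k)/(ka − k) = Tmax. This gives ka = 0.581 per h at 18 h and 0.752 per h at 36 h.

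**Share of AUC∞ reached by time t:** F(t) = 1 − (ka·e^(−kt) − k·e^(−ka·t))/(ka − k).

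| Half-life | F(48) | F(72) | F(96) | Extrapolated share, last sample 48 h | Last sample 72 h |
|---|---|---|---|---|---|
| 18 h | 0.831 | 0.933 | 0.973 | 17% | 7% |
| 36 h (assumed) | 0.593 | 0.743 | 0.838 | 41% | 26% |

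**Effect on the group.** One of six participants is truncated at t and the other five are sampled to 96 h. The geometric mean AUClast is then multiplied by (F(t)/F(96))^(1/6).

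- 18 h, last sample 48 h: (0.831/0.973)^(1/6) = 0.854^(1/6) = 0.974, a fall of 2.6%.
- 18 h, with a sample at 72 h: 0.959^(1/6) = 0.993, a fall of 0.7%.
- 36 h, last sample 48 h: 0.707^(1/6) = 0.944, a fall of 5.6%.
- 36 h, with a sample at 72 h: 0.887^(1/6) = 0.980, a fall of 2.0%.

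A leaver last sampled at 24 h lowers the group value by about 8% (18 h) or 13% (36 h). A sample 12 h later reduces this to about 5% or 9%.

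**AUC∞.** A participant last sampled at 48 h has post-peak samples at 6, 8, 12, 16, 24, 36 and 48 h, and SAP Section 10.2.2.1 needs three for λz. In the noise-free model, λz from 24, 36 and 48 h recovers AUC∞ to within 0.001% at both half-lives.

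**Part A decision.** Suppose one Group 2 participant were lost completely (5 against 6, unpaired). P(observed ratio ≥ 1.5) goes from 99.4% to 99.2%, and P(lower bound ≥ 1.5) from 75.7% to 71.5%. A truncated profile should cost less information than a participant lost outright.

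**The case against.** The strongest reply is that this visit exists for safety and that little is lost by keeping it so.

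- **Narrow window.** Leavers before 24 h are replaced. Confinement lasts to 48 h, and sites may keep participants to 96 h. SAP Section 6.5 expects few missing data. This stands, and it limits the PK point to leavers between 24 h and 96 h.
- **Small against noise.** A shift of 2.6% or 5.6% compares with a standard error of about 8% for the log mean of six (0.198/√6 = 0.081). This stands.
- **Little urine gain for the parent drug.** Protocol Section 2.2.1 puts unchanged urinary excretion below 1%. Renal clearance uses matching plasma and urine intervals, so 0–48 h remains usable, and a visit away from 72 h gives only part of an interval. This stands, though metabolite excretion in urine is a secondary endpoint.
- **Overlap with Visit 01M.** A visit at about 72 h falls where PK blood and urine receipt are already due, and Section 6.5 does not cancel them. It does not call for them either, and a visit at 60 h has no such overlap. This stands only in part.
- **Consent.** Withdrawal of consent is one route to this visit, so research sampling cannot be unconditional. This stands and shapes the fix.

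A reader might infer two stronger points. One is that a leaver without a late sample costs the trial an evaluable AUC. The sampling times and the λz rule do not support this for the 48 h leaver: AUC∞ usually remains estimable, with less precision in real data than in the model. The other is that an ECG at this visit would recover the QTcF endpoint. That endpoint is the change from screening to Day 5 (Protocol Section 3.3.2), and SAP mock-up Table 80 has only Baseline and Day 5 rows. An ECG at another time is a different observation.

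**Conclusion.** The omission is real, and nothing I found elsewhere in either document repairs it. Its weight is minor. What is lost is part of AUClast, a better-supported terminal phase and some urine intervals, for leavers between 24 h and 96 h who are not replaced. Per 48 h leaver in a group of six, the group geometric mean AUClast falls about 2.6% (half-life 18 h) or 5.6% (assumed 36 h), and a sample at about 72 h brings this to 0.7% or 2.0%. The effect on the Part A decision is small.

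These sizes rest on a one-compartment model, an assumed Tmax of 5 h and, for the larger figures, an assumed half-life. With no dropout rate in the documents, the expected loss for the trial as a whole cannot be stated. The case for acting is that the remedy costs almost nothing.

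**What to change.** Add to Protocol Section 6.5, and mirror in Appendix A, Appendix B (which has no early termination column) and SAP Table 2: if the early termination visit falls before Visit 01N is completed and the participant agrees, take 4 mL of blood for PK with the actual time recorded. Also receive any urine collected since the last interval, recording its volume and actual start and end times. State in the SAP that the plasma sample enters the non-compartmental analysis at its actual time.

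Optionally, allow the 12-lead ECG already used in the study to be done at this visit. List it as a separate early termination safety observation, and do not substitute it for the Day 5 QTcF value.

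The cost is a short protocol and schedule edit, 4 mL more blood at a venipuncture already planned and a container handover, for early leavers only.
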